	eldo_controlled	2.0; Most Recent; Effective; CURRENT	090032d580db1b91	24-Oct-2017 08:49:05
	Reason For Issue	Auto Issue		

Sodium-calcium mixed partial salt of poly(methylvinylether/maleic acid) and carboxymethylcellulose

208397

Final Clinical Protocol, 20 Oct 2017

List of tables

Table 1-1	Schedule of Activities	10
Table 2-1	Study Objectives and Endpoints.....	15
Table 13-1	Abbreviation.....	57

GlaxoSmithKline Consumer Healthcare Confidential

Template Version Effective: 22-Jun-2017

Page 9 of 62

Document Name	208397 Clinical Protocol 2.docx	Document Identifier	Effective Date
Type	Version		
eldo_controlled	2.0; Most Recent; Effective; CURRENT	090032d580db1b91	24-Oct-2017 08:49:05

Sodium-calcium mixed partial salt of poly(methylvinylether/maleic acid) and carboxymethylcellulose

208397

Final Clinical Protocol, 20 Oct 2017

SCHEDULE OF ACTIVITIES

The schedule of activities table provides an overview of the protocol visits and procedures.

The investigator may schedule visits (unplanned visits) in addition to those listed on the schedule of activities, in order to conduct evaluations or assessments required to protect the well-being of the subject.

Table 1-1 Schedule of Activities

Procedure/Assessment	Screening	Study Period		
	Visit 1	Visit 2 Treatment Period 1	Visit 3 Treatment Period 2	Visit 4 Treatment Period 3
Informed consent	X			
Review Inclusion/Exclusion criteria	X	X	X	X
Demographics	X			
Medical history	X			
Current / Concomitant treatments	X	X	X	X
Dental history	X			
OST examination edentulous	X	X ^b	X ^b	X ^b
Clean dentures ^c	X	X	X	X
Criteria for well made and fitting dentures (retention, stability, clinical acceptability and denture finish)	X			
Food migration adequacy	X			
Subject eligibility	X			
Urine pregnancy test ^e		X	X ^d	X ^d
Randomisation		X		
Subject continuance		X	X	X
Treatment application and denture insertion ^a		X	X	X
Efficacy assessment - Food occlusion testing		X	X	X
Efficacy assessment - Number of denture dislodgements		X	X	X
Photograph of dentures (subset of subjects)		X	X	X
Subject-completed questionnaire		X	X	X
Adverse events		X	X	X
Incidents	X	X	X	X
Study conclusion				X

Abbreviations: OST = Oral Soft Tissue.

Any serious adverse event assessed as related to study participation that occurs subsequent to the signing of informed consent and any adverse event that occurs subsequent to the first dose will be recorded.

a There will be a 60±5 minute wait after dentures are inserted and the commencement of the food occlusion testing.

b At visits 2-4 the OST examination will be performed before product application and also after the denture removal and peanut recovery.

c Dentures will be cleaned both prior to and after the food migratory adequacy (V1) or food occlusion testing assessment (V2-4).

d Pregnancy testing at Visits 3 and 4 are only required should more than 30 days have elapsed between the treatment visit and the previous pregnancy test.

e For females of childbearing potential per [Section 7.3.2](#).

Document Name	208397 Clinical Protocol 2.docx	Document Identifier	Effective Date
Type	Version		
eldo_controlled	2.0; Most Recent; Effective; CURRENT	090032d580db1b91	24-Oct-2017 08:49:05

Sodium-calcium mixed partial salt of poly(methylvinylether/maleic acid) and carboxymethylcellulose

208397

Final Clinical Protocol, 20 Oct 2017

1 INTRODUCTION

Denture adhesives serve to increase the retentive hold of dentures to the oral mucosa and may also reduce the ingress of food particles under the denture. Such particles can lead to irritation of the mucosa and is often a major concern to the denture wearer. Current understanding suggests that restriction of food particle ingress is achieved through a tighter denture fit provided by the denture adhesive through its ability to both adhere the denture to the mucosa and to occlude gaps between the denture and the mucosa which might otherwise be susceptible to food particle ingress ([Özcan, 2005](#)). The increased adherence to the mucosa leads to reduced movement of the denture whilst chewing, leading to a reduction in particle migration under the denture ([Tarbet, 1980](#)). Additionally, the hydration of denture adhesives through contact with saliva leads to expansion of the adhesive, occluding gaps between the denture and the underlying mucosa ([Özcan, 2005](#)). The adhesive can therefore be thought of as forming a seal along the denture borders which prevents ingress of small food particles.

Published methodologies for evaluating the performance of a denture adhesive at reducing the ingress of food particles under the denture are rather limited in numbers. Tarbet *et al* ([Tarbet, 1980](#)) had subjects subjectively rate (on a ten-point scale) whether they experienced less food particles under their dentures after eating foods including celery, steak, taffy apples and sandwiches when using a denture adhesive compared to no adhesive. This study showed a statistically significant difference ($p<0.01$) in subjective score in favour of use of adhesive compared to no adhesive use. Ahmad *et al* ([Ahmad, 2009](#); [Ahmad, 2010](#)) described a quantitative methodology based upon having fully edentulous subjects chew a prescribed amount of peanuts while wearing both their maxillary and mandibular dentures. After chewing the peanuts, the subjects brushed their dentures whilst still wearing them, rinsed with water then removed their dentures. Study staff then removed the peanut particles from the fit surfaces of the dentures and any adhesive from the dentures and the denture bearing tissues, washed and sieved the peanut particles and dried the particles prior to weighing them. This study was able to show statistically significant lower weight of peanuts collected between subjects using an adhesive compared to no adhesive use. The weight of peanut particles recovered was not reported in full, however a mean weight of 51mg and 35mg was found for maxillary dentures for the adhesive and no-adhesive treatment groups respectively.

GSK have previously sponsored studies at the University of Buffalo using a similar methodology to Ahmad ([L3510566, 2008](#); [Munoz, 2012](#)). The inclusion criterion for Kapur (Olshan modified) was, however, less stringent, allowing subjects with a score ≥ 6 to be enrolled. In this study two cream adhesives and a strip adhesive were compared to the use of no adhesive. For the cream adhesives, a total of 1.6g was used split as 1.0g for maxillary and 0.6g for mandibular dentures. The adhesive was applied as 3 short strips on the maxillary and 2 short strips on the mandibular dentures. For the strips, 3 were used for the maxillary dentures and 2 for the mandibular dentures. Peanut consumption occurred 2 hours after denture insertion. This study found there was no difference in the mass of peanut particles migrated under the dentures between any of the test groups, and that the mass of particles recovered was small, ≤ 20 mg for combined mass from both maxillary and mandibular dentures

GlaxoSmithKline Consumer Healthcare Confidential

Template Version Effective: 22-Jun-2017

Page 11 of 62

 GlaxoSmithKline	Document Name	208397 Clinical Protocol 2.docx	Document Identifier	Effective Date
	Type	Version		
	eldo_controlled	2.0; Most-Recent; Effective; CURRENT	090032d580db1b91	24-Oct-2017 08:49:05
	Reason For Issue	Auto Issue		

Sodium-calcium mixed partial salt of poly(methylvinylether/maleic acid) and carboxymethylcellulose

208397

Final Clinical Protocol, 20 Oct 2017

for each subject. Further studies by the same principle investigator (PI) did demonstrate the ability of denture adhesives to restrict the ingress of food under a dentures in studies of full (CCI [REDACTED]; [Munoz-Viveros, 2010](#)) and partial ([Munoz-Viveros, 2010](#); CCI [REDACTED]) denture wearers. These studies used modified chewing and laboratory procedures and more stringent inclusion criteria. These studies all demonstrated statistically significant reductions in food particle entrapment when using an adhesive compared to the use of no adhesive.

Following the loss of the clinical facility at University of Buffalo, GSK sponsored a study ([205915, 2016](#)) run at Salus Research using a similar methodology, but this study was unable to demonstrate a difference in peanut migration between use of an adhesive and no adhesive. A key difference between the Salus study and the previous Buffalo studies was the method of application of the adhesive to the denture.

The aim of this study is to establish a reliable methodology that is able to characterise the performance of the adhesive in terms of reducing food ingress in a food occlusion methodology where subjects are asked to eat peanuts in a controlled manner and the mass of peanut particles under the denture, post peanut consumption, is measured and compared.

This study will be conducted at Salus Research in the USA.

1.1 Mechanism of Action/Indication

Sodium-calcium mixed partial salt of poly(methylvinylether/maleic acid) and carboxymethylcellulose is currently included in a denture adhesive marketed by GSK. Denture adhesives function by forming an adhesive layer between the denture and gum surface that can act as a physical shield which can help reduce the ingress of food particles.

This study will be conducted in patients with complete maxillary and mandibular dentures.

1.2 Background and Rationale

The aim of this method development study is to assess if the changes made to the operational procedures from study 205915 result in an improved successful differentiation between the use of a denture adhesive and no denture adhesive in a model of food occlusion.

1.2.1 Study Design Rationale

Based on previous findings, the peanut occlusion methodology has demonstrated the ability to detect differences in the mass of peanut particulate measured, and this protocol will continue to use the adhesive dissolution and peanut retrieval steps utilised in GSK studies CCI [REDACTED]

Whilst the objective measure of peanut mass is the primary endpoint of interest in this study, subject derived opinion of efficacy will also be measured by means of a subject-completed questionnaire. The number of denture dislodgements reported by the subjects during the chewing of the peanuts will also be collected and analysed and this, and the questionnaire data, will be used to support the findings of the peanut mass measure.

 GlaxoSmithKline	Document Name	208397 Clinical Protocol 2.docx		
	Type	Version	Document Identifier	Effective Date
	eldo_controlled	2.0; Most Recent; Effective; CURRENT	090032d580db1b91	24-Oct-2017 08:49:05
	Reason For Issue	Auto Issue		

Sodium-calcium mixed partial salt of poly(methylvinylether/maleic acid) and carboxymethylcellulose

208397

Final Clinical Protocol, 20 Oct 2017

Dentures are unique to each individual. Therefore, the most efficient approach to evaluating their performance with different adhesives or 'no adhesive' is a within subject comparison (i.e. a crossover design). Denture adhesive is used to secure dentures in the mouth. It forms a barrier that prevents food from entering the area between dentures and the edentulous ridge. This study will assess the objective measure of food occlusion while chewing peanuts as measured by mass of peanuts retrieved, as well as subjective measures of efficacy as measured by questionnaire data.

Peanuts were chosen as the model food in this methodology because they are a brittle food that, when masticated, break into small particles that can be recovered. Peanuts have therefore been retained as a model food for this study and to allow comparison with previous data.

In order for subjects to be eligible they must report that they get food trapped under their dentures and this must be evident following the standardised peanut migration adequacy testing at screening (Visit 1). This is to ensure that measurable amounts of peanut particles migrate under the denture when no denture adhesive is being used. Whilst peanut allergy is specific, peanuts supplied for this study may themselves be contaminated with other nuts owing to the manufacturing process. Therefore, subjects with any nut allergy are excluded from this study. Subjects with temporomandibular joint disorders are excluded should the investigator believes that this could affect the subject's participation, principally regarding the ability for the subject to adequately chew the peanuts. Subjects who use or have ever used bisphosphonate medications are specifically excluded from this study owing to the enhanced risk of bisphosphonate-related osteonecrosis of the jaw (BRONJ) that is associated with reduced tissue tolerance to function with removable prostheses ([Saldanha, 2012](#)). Subjects in this study must be habitual wearers of full dentures to ensure that they are familiar with chewing with their dentures in place. Subjects who are xerostomic are excluded since the proper function of denture adhesives requires adequate hydration from saliva.

During this study, photographs of dentures with peanut particles attached will be taken. The purpose of this is to gather representative photographs of the dentures to aid in the dissemination and interpretation of the results, e.g. in manuscript preparation. No personally identifiable information will be included in these photographs. Demography information will be recorded as part of this study, including age, race and gender. In accordance with the United States Food and Drug Administration (US FDA) guidelines ([FDA, 2005](#)) the ethnicity of subjects will also be captured.

An oral soft tissue (OST) examination will be conducted at each treatment visit before treatment is applied to ensure the subject's oral health is sufficient to allow the subject to complete the assessments at that visit. A further OST exam will be performed at each treatment visit after the completion of assessments to assess for possible AEs.

Whilst blinding is an important consideration for any clinical study, the objectives of this study are not to investigate product efficacy, but to develop a methodology. To fulfil the objectives of this study it is not possible to adequately maintain blinding and therefore this study will be conducted open label.

 GlaxoSmithKline	Document Name	208397 Clinical Protocol 2.docx		
	Type	Version	Document Identifier	Effective Date
	eldo_controlled	2.0; Most Recent; Effective; CURRENT	090032d580db1b91	24-Oct-2017 08:49:05
	Reason For Issue	Auto Issue		

Sodium-calcium mixed partial salt of poly(methylvinylether/maleic acid) and carboxymethylcellulose

208397

Final Clinical Protocol, 20 Oct 2017

The Kapur-Olshan index is a composite score based upon stability and retention ratings for the maxillary and mandibular dentures ([Kapur, 1967](#); [Olshan, 1992](#)). In this study, subject recruitment will be targeted to achieve approximately equal numbers of subjects in the low and high Kapur-Olshan groups. The low Kapur-Olshan group is defined as a composite Kapur-Olshan score of 6-14 (clinically fair and good dentures) and the high Kapur-Olshan score as 15-18 (clinically very good dentures), values derived from consideration of previous study data ([205915, 2016](#)). The purpose of this analysis is to explore the optimum inclusion criteria for future studies. Subjects presenting with a very low Kapur-Olshan score at Screening (<6), defined as "Clinically Poor" ([Olshan, 1992](#)), will be excluded from this study.

Denture adhesive achieves its function by physical means and once completely removed from the denture does not have any residual effects. Therefore, the 2-30 day period between each test day is considered adequate rest for the oral soft tissues from the stresses of mastication encountered in this study.

Marketed denture adhesives are commonly extruded by the consumer onto the denture either through a flat ribbon nozzle with instructions for use to "dab" the product onto the denture (the conventional application pattern) or through a finer nozzle that enables the adhesive product to be more precisely applied so allowing a continuous bead of product around the borders of the dentures (continuous strips application pattern). In this method development study both application methods will be evaluated, with the adhesive applied via a syringe, to assess if the methodology is compatible with either or both application methods. The use of the syringe allows for greater control of dose and application pattern and is consistent with previous studies.

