7.1.3 Well-Fit Assessment, Kapur (Olshan Modification) Index

Each denture (upper and lower) will be examined for retention and stability using the Kapur Index (Olshan Modification) ([Kapur, 1967](#); [Olshan, 1992](#)) by an examiner with expert knowledge of prosthodontics. A sum score (upper + lower) of ≥ 6 is required for inclusion.

Retention:

With gloved hands, the examiner will attempt to unseat the upper and lower denture by applying an opposing vertical force at the canine/lateral incisor region of the denture. The examiner will score retention as 0 - 5 using the following criteria:

5= Excellent- denture offers excellent resistance to vertical pull and lateral force.

4= Very Good- denture offers very good resistance to vertical pull and lateral force.

3= Good- denture offers moderate resistance to vertical pull and lateral force.

2= Fair- denture offers moderate resistance to vertical pull and little or no resistance to lateral forces.

1= Poor- denture offers slight resistance to vertical pull and little or no resistance to lateral force.

0= No retention- when the denture is seated in place, it displaces itself.

Stability:

With gloved hands, the examiner will attempt to rock the seated dentures by placing alternate horizontal force at the cuspid and contralateral molar regions of the upper and lower dentures.

The examiner will score denture stability as 0 - 4 using the following criteria:

4= Excellent- when denture base offers no rocking on its supporting structures under pressure.

3= Good- when denture base has very slight rocking on its supporting structures under pressure.

2= Fair- when denture base has slight rocking on its supporting structures under pressure.

1= Poor- when denture base has moderate rocking on its supporting structures under pressure.

0= No stability- when denture base has extreme rocking under pressure.

Sum score (upper + lower denture) of <6 = dentures with poor retention and stability.

 GlaxoSmithKline	Document Name	208397 Clinical Protocol 2.docx		
	Type	Version	Document Identifier	Effective Date
	eldo_controlled	2.0; Most Recent; Effective; CURRENT	090032d580db1b91	24-Oct-2017 08:49:05
	Reason For Issue	Auto Issue		

Sodium-calcium mixed partial salt of poly(methylvinylether/maleic acid) and carboxymethylcellulose

208397

Final Clinical Protocol, 20 Oct 2017

Sum score (upper + lower denture) 6-9 = dentures with fair retention and stability.

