3.2 Subgroups/Stratifications

The subgroups defined in this study are as follows:

Low Kapur-Olshan group: Defined as a composite Kapur-Olshan score of 6-14 (clinically fair and good dentures) at screening.

High Kapur-Olshan group: Defined as a composite Kapur-Olshan score of 15-18 (clinically very good dentures) at screening.

Exploratory analysis will be performed on the above defined subgroups.

Stratification factors are not defined in this study.

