4.6 Additional Analysis

Adjusted means for mass of peanuts recovered from mandibular, maxillary (Table 16.1.9.2.1) and combined (Table 16.1.9.1.1) dentures, along with 95% confidence interval (CI) will also be reported by treatment group. These will be derived from a mixed model with period and treatment as fixed effects and subject as a random effect. The pair-wise comparisons will be performed and corresponding treatment differences, SE and 95% CI will be presented for all patients in ITT population. No p-value will be reported.

Using the same model as above, a subgroup analysis will be also conducted in low and high Kapur-Olshan groups of subjects. Adjusted means of combined masses of peanuts recovered from mandibular and maxillary denture, along with 95% CI will be presented by treatment groups for each sub-group (Table 16.1.9.3.1) for all patients in ITT population.

These results will be reported in the statistical appendix as part of CSR.

The assumptions underlying the mixed model will be examined using appropriate statistical method and if necessary, a suitable transformation of data or alternative non-parametric method based on ranks will be applied to obtain the inferential statistics. Hodges-Lehmann estimates of median of differences and Hodges-Lehmann 95% confidence intervals will be calculated.

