Sodium-calcium mixed partial salt of poly (methylvinylether/maleic acid) and carboxymethylcellulose

208397

Final Statistical Reporting and Analysis plan, 14 DEC 2017

Protocol: 208397

Program Run Date: DDMMYYYY

Table 14.1.4.1
Demographic and Baseline Characteristics
Safety Population

Study Population: Safety Population (N=xxx)

	Overall (N = xxx)
SEX n (%)	
MALE	xxx (xx.x)
FEMALE	xxx (xx.x)
RACE n (%)	
AFRICAN AMERICAN/AFRICAN HERITAGE	xxx (xx.x)
AMERICAN INDIAN OR ALASKAN NATIVE	xxx (xx.x)

ETHNICITY n (%)	
HISPANIC OR LATINO	xxx (xx.x)
NOT HISPANIC OR LATINO	xxx (xx.x)
AGE (YEARS)	
n	xx
MEAN	xx.x
SD	xx.xx
MEDIAN	xx.x
MINIMUM	xx
MAXIMUM	xx
CURRENT DENTURE AGE (YEARS)	
n	xx
MEAN	xx.xx
SD	xx.xxx
MEDIAN	xx.xx
MINIMUM	xx.x
MAXIMUM	xx.x
KAPUR-OLSHAN SUBGROUP n (%)	
LOW (SCORE 6-14)	
6	xxx (xx.x)
7	xxx (xx.x)

Sodium-calcium mixed partial salt of poly (methylvinylether/maleic acid) and carboxymethylcellulose

208397

Final Statistical Reporting and Analysis plan, 14 DEC 2017

HIGH (SCORE 15-18)
15
16

xxx (xx.x)
xxx (xx.x)
xxx (xx.x)

Program: xxxxx.sas

Page x of y
Source: Filename

Programming Note: The categories for all the races will be displayed. Similar table will be generated for ITT population.

All individual score of Kapur-Olshan groups will be summarized.

Sodium-calcium mixed partial salt of poly (methylvinylether/maleic acid) and carboxymethylcellulose

208397

Final Statistical Reporting and Analysis plan, 14 DEC 2017

Protocol 208397

Program Run Date: DDMMYYYY

Table 14.2.1
Study Product Compliance
Intent-to-Treat Population

Study Population: Intent-to-Treat Population (N=XXX)	Statistics	Conventional Application	Continuous Strip Application
		(N = XXX)	(N = XXX)
WEIGHT (g) OF ADHESIVE	n	XXX	XXX
	MEAN	X.XXX	X.XXX
	SD	X.XXXX	X.XXXX
	MEDIAN	X.XXX	X.XXX
	MINIMUM	X.XX	X.XX
	MAXIMUM	X.XX	X.XX
LOWER	n	XXX	XXX
	MEAN	X.XXX	X.XXX
	SD	X.XXXX	X.XXXX
	MEDIAN	X.XXX	X.XXX
	MINIMUM	X.XX	X.XX
	MAXIMUM	X.XX	X.XX
UPPER	n	XXX	XXX
	MEAN	X.XXX	X.XXX
	SD	X.XXXX	X.XXXX
	MEDIAN	X.XXX	X.XXX
	MINIMUM	X.XX	X.XX
	MAXIMUM	X.XX	X.XX
COMBINED (LOWER + UPPER)	n	XXX	XXX
	MEAN	X.XXX	X.XXX
	SD	X.XXXX	X.XXXX
	MEDIAN	X.XXX	X.XXX
	MINIMUM	X.XX	X.XX
	MAXIMUM	X.XX	X.XX

Program: xxxxxx.sas

Page x of y
Source: Filename

Sodium-calcium mixed partial salt of poly (methylvinylether/maleic acid) and carboxymethylcellulose

208397

Final Statistical Reporting and Analysis plan, 14 DEC 2017

Protocol 208397

Program Run Date: DDMMYYYY

Table 14.2.2.1

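### The Kapur-Olshan score enters the efficacy analysis only as one 14/15 split, so the plan cannot show how the adhesive effect varies within scores 6 to 14

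*Protocol*

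**What the plan says.** Protocol 1.2.1 gives the reason for analysing by denture fit: "The purpose of this analysis is to explore the optimum inclusion criteria for future studies". A recruitment quota of 40-60% per group supports it (Protocol 4.3 and 10.1).

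SAP 3.2 fixes two groups: "Low Kapur-Olshan group: Defined as a composite Kapur-Olshan score of 6-14 (clinically fair and good dentures) at screening" and "High Kapur-Olshan group: Defined as a composite Kapur-Olshan score of 15-18 (clinically very good dentures) at screening".

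The score is then used for efficacy in two places:

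- Descriptive statistics of combined peanut mass by treatment within each group (Protocol 10.2.7; SAP 4.5.2, Table 14.2.5).
- The mixed model with period, treatment and random subject, repeated by group. SAP 4.6 says "a subgroup analysis will be also conducted in low and high Kapur-Olshan groups of subjects". The shell of Table 16.1.9.3.1 shows adjusted means and the three pairwise treatment differences, with SE and 95% CI, separately for each group.

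Protocol 7.1.3 itself divides the low group in two: "Sum score (upper + lower denture) 6-9 = dentures with fair retention and stability", with 10-14 rated good and scores above 14 very good.

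Individual scores are kept. The note under the shell of Table 14.1.4.1 in SAP Appendix 1 says "All individual score of Kapur-Olshan groups will be summarized", and Listing 16.2.4.2 gives them by subject.

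**The concern.** The purpose is to learn which dentures the next study should admit. That depends on how the difference between conventional application and no adhesive changes with fit. The plan gives two sets of treatment differences, one on each side of a preset cut.

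Three things are absent:

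- a model term for the score, or for treatment by score;
- a reported contrast between the two groups. A reader could form one from the two SEs, since no subject is in both groups, but no display shows it;
- any separation of the fair and good bands, so a question such as whether dentures scoring 6-9 behave differently from those scoring 10-14 is not examined.

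At stake is how useful the result is for designing later studies. The primary summary of peanut mass is unaffected.

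**Working it through.** **No figure to reproduce.** Protocol 10.1 says that no formal sample size calculation was made (part of that section is redacted). No effect size, SD or score distribution is readable, so the distributions below are assumptions.

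**Scale.** Per denture, "The examiner will score retention as 0 - 5" and stability is scored 0-4, so two dentures give at most 2 × (5 + 4) = 18. Entry requires at least 6. That leaves nine possible scores in the low group and four in the high group. With 48 subjects and a 40-60% quota, each group has 19.2 to 28.8, or about 19 to 29. An even split gives 24 / 9 = 2.7 low-group subjects per score.

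**What two group means can show.** Assume scores flat within each group and a treatment effect that steps from 0 to 1 at score c. For c up to 15 the low mean is (15 − c)/9 and the high mean is 1. For c of 15 or more the low mean is 0 and the high mean is (19 − c)/4.

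| Step at | Low mean | High mean | High minus low |
|---|---|---|---|
| 10 | 0.56 | 1.00 | 0.44 |
| 13 | 0.22 | 1.00 | 0.78 |
| 15 | 0.00 | 1.00 | 1.00 |
| 16 | 0.00 | 0.75 | 0.75 |
| 17 | 0.00 | 0.50 | 0.50 |

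Steps at 13 and 16 give almost the same contrast. The pair of means would show the side of the cut if the starting level and the step size were known, but they are not. A straight line also fits: the mean scores are 10 and 16.5, so a slope of 0.78 / 6.5 = 0.12 per point reproduces both means for the step at 13.

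**Slope information kept if the effect is linear.** The share kept by the high/low indicator is its squared correlation with the score. With p the share in the high group:

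R² = p(1 − p)D² / [p(1 − p)D² + (1 − p)V_L + pV_H]

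For flat scores, D = 16.5 − 10 = 6.5, V_L = (81 − 1)/12 = 6.67 and V_H = (16 − 1)/12 = 1.25.

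- p = 0.5: 10.56 / (10.56 + 3.96) = 0.727, equivalent to 48 × 0.727 = 34.9 subjects
- p = 0.4: 10.14 / (10.14 + 4.50) = 0.693
- p = 0.6: 10.14 / (10.14 + 3.42) = 0.748

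Other assumed shapes (range over p = 0.4 to 0.6, except the normal):

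| Assumed scores | R² |
|---|---|
| Both groups piled toward the cut | 0.61-0.67 (0.649 at p = 0.5) |
| Discretised normal centred at 14-15 | 0.63-0.67 |
| Low group only 10-14, high group flat | 0.74-0.76 |
| Low group toward 6, high group toward 18 | 0.83-0.87 |
| Low group only 6-9, high group flat | 0.94 |

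Across these shapes the loss runs from about 6% to 39%. If the effect steps exactly at 14/15, the indicator is the right predictor and nothing is lost.

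**Precision of a continuous-score model.** Take 48 complete subjects with flat scores, p = 0.5, mean score 13.25 and score variance 14.52. Ignoring period terms, the SE of the fitted difference at score s, in units of the SD of the within-subject difference, is √[1/48 + (s − 13.25)²/(48 × 14.52)].

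- s = 6: √(0.0208 + 0.0754) = 0.31
- s = 10: √(0.0208 + 0.0152) = 0.19
- s = 18: √(0.0208 + 0.0324) = 0.23
- low-group mean, for comparison: 1/√24 = 0.20

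The gain is a view of how the effect changes with score, not better precision at any one score.

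**The case against.** The plan delivers the objective as tabulated. Protocol Table 2-1 and SAP 1.2 ask for performance in the low and high subgroups, in a method development study with no success criterion. The aim is to explore, and no section promises to locate a threshold. The cut is also reasoned: Protocol 1.2.1 describes "values derived from consideration of previous study data", and it coincides with the index's own boundary for very good dentures in 7.1.3. Finally, 48 subjects cannot support a precise dose-response type curve over 13 scores.

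All of that stands, and it rules out two inferences a reader might draw. One is that the cut is arbitrary, which the stated basis contradicts. The other is that the analysis says nothing about inclusion limits. The split shows how the method performs with scores 15-18 set apart, so it bears directly on a limit at 14/15. Scores below 6 are excluded, so no analysis of these data could compare a lower limit of 6 with anything beneath it.

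The objection does not answer the narrower point. Nothing planned describes variation within 6-14, and exploration in a small sample is a reason to use the whole score. Listings 16.2.4.2 and 16.2.6.1 hold each subject's score and masses, so a later look is possible. But the study is open label with no blinded team members (Protocol 5.1), and a relation or cut chosen after the results are seen would be data-driven.

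**Conclusion.** The point holds as a cheap improvement to an exploratory analysis reported in a statistical appendix. It is not an error in the plan. That the planned analysis cannot show variation within 6-14 follows from the group definitions and the model terms, and needs no assumption about information loss.

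The size does need assumptions. With a linear effect, and scores flat within groups or peaked near the cut, roughly 65-75% of the slope information is kept. A reader might infer that the split simply throws away about a quarter of the information. The documents do not support that as a fixed figure, since they give neither a score distribution nor a reason to expect linearity.

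**What to change.** Keep the two-group tables. Add to SAP 4.6, before results are seen, one exploratory mixed model on all ITT subjects for combined peanut mass: treatment, period, continuous screening score and treatment × score as fixed effects, with subject as a random effect. Report:

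- the slope on score of the conventional-minus-no-adhesive difference, with 95% CI;
- the fitted difference, with 95% CI, at a few scores named in advance and limited to the observed range;
- a plot of each subject's within-subject difference against score, to check linearity.

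No p-value is needed, in line with SAP 4.6. The cost is one model and one figure on data already collected, with no change to visits or recruitment. The limits should be stated with the result: the model assumes a smooth relation, it will be imprecise at the extreme scores with about 48 subjects, and it describes a trend without locating an exact threshold.
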